3.0 STUDY DESIGN

The proposed study is a randomized, placebo-controlled, two-arm, partial cross-over, single-site, pilot study comparing the effect of 12 weeks of DP or placebo on immune activation and inflammation. The study will enroll approximately 40 HIV-1-infected subjects, age 18 years or older, who have been on ART for at least 12 months prior to study entry and have HIV-1 RNA <50 copies/mL for at least 12 months prior to study entry. Subjects will be randomized equally to two regimens:

Arm A: Dipyridamole 100 mg four times daily for 24 weeks

or

Arm B: Dipyridamole placebo capsule four times daily for 12 weeks, then Dipyridamole 100 mg four times daily for 12 weeks.

Each subject will be enrolled for 28 weeks. Accrual is expected to be completed in approximately 18 months.

In addition, this study will include Rectal Tissue evaluations in 20 subjects (10 per arm). Flexible sigmoidoscopy with biopsies will be done at Entry/Week 0 and Weeks 12, 24, and 28.

The primary endpoints will be change from baseline to week 12 in plasma levels of sCD163, sCD14, and IL-6. Secondary endpoints will include changes in immune activation as measured in blood (%HLA-DR+CD38+CD8+ and CD4+ T-cells and %CD69+CD25+ CD8+ and CD4+ T-cells) and rectal tissue (HLA-DR+CD45RO+CD4+ T-cells, gut-homing CD4+ T-cells), cell-associated HIV-1 RNA and total DNA, and safety and tolerability of DP in HIV-1-infected adults.

Assessment of the primary and secondary endpoints at Week 24 will be conducted to gather additional longitudinal data. Arm A subjects will provide data on the durability of the effect of DP on immune activation, as well as safety and tolerability. Arm B subjects will receive DP from week 12 to week 24 and will enhance the power of the study to detect an effect of DP as well provide additional safety and tolerability data.

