9.2 Endpoints

9.2.1 Primary Endpoints

- Change in Plasma level of sCD14 from baseline to week 12.
- Change in Plasma level of sCD163 and IL-6 from baseline to week 12.

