9.4 Sample Size and Accrual

There will be 40 subjects (20 per arm) randomized to either DP 100 mg 4 times daily or matching placebo, and it is assumed that no more than 10% of participants will be excluded from the primary analysis due to any reason. sCD14 will be the main primary outcome, while sCD163 and IL-6 will be treated as other key outcomes of interest. As a result, the hypothesis for sCD14 will be tested at the 5% significance level and will be the basis for our power analysis. sCD163 and IL-6 will also be tested at the 5% significance level each. Based on the assumption that none of the 40 subjects are excluded from the primary analysis for any reason, we will have 80% power to detect standardized mean difference of 0.909 between treatment arms for the sCD14. In terms of clinically meaningful effects, this translates to a difference of 0.49×10^6 pg/mL in sCD14 between arms at 12 weeks assuming similar standard deviation seen in preliminary data (standard deviation is 0.54×10^6 pg/mL for sCD14). In the more realistic situation that 10% of subjects are excluded (18 per arm), we will have 80% power to detect standardized mean difference of 0.961 between treatment arms for the primary outcome. In terms of clinically meaningful effects, this translates to a difference of 0.52×10^6 pg/mL in sCD14 between arms at 12 weeks assuming similar standard deviations seen in preliminary data.

Because the ANCOVA model will adjust for baseline sCD14 as well as CD4 cell count (neither of which are expected to be related to treatment arm), it's likely that there will be sufficient power to detect even smaller effects than what is expected.

It is anticipated that subjects will accrue to the study at a rate of 2-3 subjects per month. At this rate, the study should fully accrue within 18 months after the first subject enrolls.

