9.5 Primary Analyses

As this is a pilot study of biologic activity, our primary analysis of efficacy will be an as-treated analysis, limited to subjects who have data for baseline and week 12, and remain on study treatment through week 12 with no more than 7 consecutive days of medication

missed, and did not change ART or use prohibited medications or have virologic failure during this time period. To preserve the study power in the case of greater than 10% missing data due to discontinuation/non-adherence, additional subjects may enroll, at discretion of the protocol team, to replace subjects who are discontinued or non-adherent to study product or scheduled study visits prior to week 12. Therefore the total sample size may exceed 40 at the end of the study.

Changes from baseline to week 12 in sCD14, sCD163, and IL-6 (as well as all secondary and exploratory outcomes) will be summarized by means, medians, standard deviations, and 95% confidence intervals for each treatment arm. We will compare the two study arms at baseline with respect to clinical characteristics as well as subject demographics. Any baseline covariates that cause imbalance at the 5% significance level will be included in the primary analyses. Our primary analysis will utilize an Analysis of Covariance (ANCOVA) model of the primary outcomes, which compares the outcomes at 12 weeks between arms (placebo/DP) after adjusting for baseline activation (or plasma level) and CD4 cell count. If any of the primary outcomes violate assumptions of normality, suitable transformations will be investigated. If no transformation can be used, between-arm comparisons on 12 week change in sCD14, sCD163, and IL-6 will be assessed by the Wilcoxon rank sum test.

Statistical significance for the primary analysis of sCD14 will be tested using a two-sided $\alpha = 0.05$. The other key outcomes of sCD163 and IL-6 will each be tested at 0.05 as well.

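### The documents disagree on whether there are three primary endpoints or one, and leave open what a significant sCD163 or IL-6 result would mean if sCD14 fails

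*Combined protocol and SAP*

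**What the plan says.** Two descriptions of the primary endpoint stand side by side.

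**Three primary endpoints.** Section 3.0 states: "The primary endpoints will be change from baseline to week 12 in plasma levels of sCD163, sCD14, and IL-6". The primary objective in 1.2.1 names the same three markers. Section 9.2.1, headed as the primary endpoints, gives sCD14 one bullet and then adds a second: "Change in Plasma level of sCD163 and IL-6 from baseline to week 12". The synopsis mentions the three together and sets them apart from the secondary endpoints. Sections 1.3.6, 9.5 and 9.7 refer to primary measures, outcomes or endpoints in a way that fits more than one. The secondary list in 9.2.2 does not contain sCD163, and IL-6 appears there only as a correlate of the plasma drug level.

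**One main primary endpoint and two others.** Section 9.4 states: "sCD14 will be the main primary outcome, while sCD163 and IL-6 will be treated as other key outcomes of interest". It continues that "the hypothesis for sCD14 will be tested at the 5% significance level and will be the basis for our power analysis", and then that "sCD163 and IL-6 will also be tested at the 5% significance level each". Section 9.5 repeats the arrangement: "Statistical significance for the primary analysis of sCD14 will be tested using a two-sided" 0.05, followed by "The other key outcomes of sCD163 and IL-6 will each be tested at 0.05 as well".

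No section gives a multiplicity adjustment, a testing sequence, or a statement of what may be claimed on sCD163 or IL-6 if sCD14 is not significant.

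**The concern.** Section 9.4 uses the ranking of sCD14 as its reason for giving that marker the 5% level, and then gives the other two the same level. The ranking therefore settles the power calculation but not the interpretation. A report that follows 3.0 and 9.2.1 could present a significant IL-6 or sCD163 result, with sCD14 not significant, as a positive primary endpoint. A report that follows 9.4 and 9.5 would present the same data as a trial whose main endpoint was not met. The plan should decide between these before the data are seen.

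The case is realistic. The trial has 80% power only for a large sCD14 effect (0.909 or 0.961 SD), so a non-significant sCD14 result beside a significant result on another marker could well occur.

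**Working it through.** **Inputs.** Two-sided alpha of 0.05 for sCD14 (9.5); 0.05 each for sCD163 and IL-6 (9.4, 9.5); 20 per arm, or 18 per arm after 10% exclusions (9.4); SD of sCD14 0.54 × 10^6 pg/mL (9.4). The correlation between the three tests is not in the documents. It is an assumption here, varied from 0 to 0.9. For the planned ANCOVA, the relevant correlation is that between the baseline-adjusted week-12 values.

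**Step 1: the plan's own figure.** Section 9.4 says that "we will have 80% power to detect standardized mean difference of 0.909 between treatment arms for the sCD14" with 20 per arm. Power of a two-sample t-test from the noncentral t distribution, with noncentrality d × √(n/2):

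- n = 20 per arm, d = 0.909: 79.99%. In units, 0.909 × 0.54 = 0.491 (stated 0.49).
- n = 18 per arm, d = 0.961: 79.98%. In units, 0.961 × 0.54 = 0.519 (stated 0.52).

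The stated power is reproduced. It rests on a full two-sided 5% for sCD14 alone.

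**Step 2: error rate of the sCD14 test.** One test at two-sided 0.05 has a 5.0% error rate. The other two tests do not change it.

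**Step 3: error rate if any of the three could count as a primary finding.** With independent tests and no effect on any marker:

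1 − (1 − 0.05)^3 = 1 − 0.857375 = 14.3%.

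With a common correlation ρ and c = 1.96:

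1 − ∫ [Φ((c − √ρ x)/√(1 − ρ)) − Φ((−c − √ρ x)/√(1 − ρ))]^3 φ(x) dx.

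Subtracting the 5.0% for sCD14 gives the chance that sCD14 is not significant but sCD163 or IL-6 is, falsely. This is the outcome that the plan leaves undefined.

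| Assumed ρ | At least one of three | sCD163 and/or IL-6 only |
|---|---|---|
| 0 | 14.3% | 9.3% |
| 0.3 | 13.6% | 8.6% |
| 0.5 | 12.5% | 7.5% |
| 0.7 | 10.9% | 5.9% |
| 0.8 | 9.8% | 4.8% |
| 0.9 | 8.4% | 3.4% |

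A simulation of t-tests with 18 per arm (200,000 runs per correlation) gave 14.3%, 13.7%, 12.6% and 11.1% at ρ = 0, 0.3, 0.5 and 0.7.

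**Step 4: what the alternative remedy would cost.** If all three were kept as primary with Bonferroni (0.05/3 = 0.0167 each), power for sCD14 at the stated effects would fall from 80% to 64.5% (20 per arm) or 64.3% (18 per arm). The difference detectable with 80% power would rise to 1.064 SD (1.064 × 0.54 = 0.57 × 10^6 pg/mL) or 1.126 SD (1.126 × 0.54 = 0.61 × 10^6 pg/mL).

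**The case against.** A reader might infer that the endpoints are unordered and that the trial's primary error rate is therefore 11% to 14% instead of 5%. The documents do not support that. Section 9.4 names sCD14 as the main one in advance and bases the power on it. Section 9.5 repeats the distinction in the very sentence that gives the other two their 5%. The separate bullets in 9.2.1 fit the same ranking. The plan claims no error control across the three and states no rule that success on any one suffices, so no stated error rate is shown to be false. The 11% to 14% depends on such a rule being adopted and on correlations that are assumed.

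A reader might also infer that a formal multiplicity procedure is required. Section 9.5 describes a pilot study of biologic activity, and 9.6 openly uses a nominal 5% for every secondary analysis. Unadjusted testing of supportive markers is a defensible and disclosed choice in that setting.

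Both objections stand, and they limit the point. They do not remove it: 3.0 and 9.2.1 give the label primary to two markers that 9.4 treats as something else, and no sentence says which governs when sCD14 fails. If the two are meant to be supportive, the documents should say so.

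**Conclusion.** There is a real inconsistency in labelling, with an undefined consequence. The test of sCD14 is sound: 5% error, and 80% power at the stated effects. The gap concerns only what a lone significant sCD163 or IL-6 result may be called. If it could be called a primary finding, the chance of at least one false primary finding, with no effect on any marker, would be about 11% to 14% for assumed correlations of 0.7 down to 0, and 8.4% at 0.9. Of this, 9.3% down to 5.9% (3.4% at 0.9) comes from the two other markers alone. For a self-described pilot this is a modest matter, but it is cheap to settle. Section 9.7 says that the primary markers are assayed in batch after follow-up ends, so the rule can be fixed before any of those results exist.

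**What to change.** - Name sCD14 change to week 12 as the single primary endpoint wherever the three are treated as primary: synopsis, 1.2.1, 1.3.6, 3.0, 9.2.1, 9.5 and 9.7. Section 9.4 already points this way.
- List sCD163 and IL-6 as key secondary endpoints in 9.2.2.
- In 9.4 and 9.5, state that the nominal 5% tests of sCD163 and IL-6 are supportive and cannot make the primary result positive if sCD14 is not significant.
- Optional for a pilot: test sCD163 and IL-6 by Holm only after sCD14 is significant, and otherwise report estimates with 95% confidence intervals. Without this step, the chance that at least one of the two supportive tests is falsely significant stays at 9.75% if independent and 8.35% at correlation 0.7. That is acceptable if they are plainly labelled as supportive.

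The cost is wording in the sections listed, and no patients. The downside is that no primary claim can rest on sCD163 or IL-6 alone. Alpha and power for sCD14 are unchanged, whereas Bonferroni over three would cut its power to about 64%.

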9.6 Secondary Analyses

Changes from baseline to week 12 and week 24 in other secondary and exploratory endpoints including measurements of immune activation, systemic inflammation, and residual virus in blood and rectal tissue, change in pre- and post-bronchodilator FEV₁, and percent FMD (see 9.2.2 and 9.2.3) will be summarized by means, medians, standard deviations, and 95% CIs for each of the treatment arms. As in the primary analysis, between-arm comparisons will be made using either an ANCOVA model or the Wilcoxon rank sum test. For secondary outcomes with more frequent measurements (i.e. baseline, 4, 12 week), longitudinal models such as Generalized Estimating Equations (GEE) will be used to compare the trajectories across time between treatment arms. Included in the model will be predictor variables for week, treatment group, and their interaction.

The study design allows for an additional 12 weeks of follow up in which the placebo arm crosses over to DP 100 mg 4 times daily for 12 weeks. As an exploratory measure, the trajectories of T cell activation and IL-6 expression for these subjects will be analyzed using a generalized linear mixed model with covariates for week (defined as time since initiating placebo/DP), drug (placebo/DP), and their interaction. The effects of long-term and short-term DP on T cell activation will be quantified using an ANCOVA model, similar to the primary analysis.

Safety will be evaluated by summarizing the number and frequency of Grade ≥ 2 adverse events within each study arm. Comparisons between study arms will be done

using Fisher's exact test at each study visit.

Statistical significance for each of the secondary analyses will be tested using the nominal 5% type I error rate.

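### Section 9.6 names GEE for the longitudinal secondary outcomes without a small-sample correction; run in its default form with 18–20 subjects per arm, its nominal 5% interaction tests would run at about 6–8%

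*Combined protocol and SAP*

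**What the plan says.** Section 9.6 (Secondary Analyses) first assigns ANCOVA or the Wilcoxon rank sum test to between-arm comparisons of the secondary and exploratory endpoints. It then adds a further analysis for those secondary outcomes that have a week-4 value as well as baseline and week 12: "longitudinal models such as Generalized Estimating Equations (GEE) will be used to compare the trajectories across time between treatment arms". On the model terms it says: "Included in the model will be predictor variables for week, treatment group, and their interaction". The section closes with: "Statistical significance for each of the secondary analyses will be tested using the nominal 5% type I error rate".

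Section 9.4 gives the size: "There will be 40 subjects (20 per arm) randomized to either DP 100 mg 4 times daily or matching placebo". It also gives a reduced case: "In the more realistic situation that 10% of subjects are excluded (18 per arm"). So the GEE would have 36 to 40 independent subjects.

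The plan does not state the working correlation, the type of standard error (sandwich, bias-corrected or model-based), the coding of week (linear or categorical), the type of test (Wald or score), the reference distribution or any correction for few subjects.

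**The concern.** The usual GEE test divides the estimate by an empirical sandwich standard error and refers the result to the normal or chi-square distribution. Both steps rely on a large number of independent subjects. With 18–20 per arm the sandwich variance is biased downward, and the normal reference ignores the error in estimating it. Both push the rejection rate above the stated 5%.

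The rule could reach most secondary outcomes. The schedule in Section 6.1 collects stored plasma and PBMC, and performs FMD, at entry, week 4 and week 12. Section 9.2.2 lists 14 change endpoints drawn from these: four T-cell activation, two monocyte, five soluble, one FMD and two Ki-67. If all 14 were null, the expected number of false positives would be 14 × 0.05 = 0.70 at the nominal level, and 14 × 0.076 = 1.06 at a true level of 7.6% (the 2-df figure for 20 per arm below). The absence of multiplicity control is a separate matter, but this excess adds to it.

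**Working it through.** **Inputs from the documents.** Arms of n = 20 or 18 (Section 9.4); three visits at weeks 0, 4 and 12, terms for week, arm and their interaction, and a 5% level (Section 9.6). A two-sided test is stated for the primary analysis (Section 9.5) and assumed here.

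**Inputs assumed.** Normal data; within-subject correlation of 0.5 to 0.8, exchangeable or decaying with time; complete data.

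**Step 1: the plan's own figures.** The plan gives no actual error rate for GEE. Its power figures do reproduce. A two-sample t-test (noncentral t) has 79.99% power at a standardized difference of 0.909 with 20 per arm, and 79.98% at 0.961 with 18. Also 0.909 × 0.54 = 0.49 and 0.961 × 0.54 = 0.52 (× 10^6 pg/mL), as stated.

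**Step 2: closed form, 1 df.** With complete data, equal arms and common visit times, the sandwich variance of the between-arm difference in mean change (or in mean slope) is the usual unbiased variance times (n − 1)/n, because it divides by n. The Wald z test therefore rejects when |t| > 1.96 × √((n − 1)/n), where t has 2n − 2 df.
- n = 20: 1.96 × √(19/20) = 1.910; 2·P(t38 > 1.910) = 6.37%.
- n = 18: 1.96 × √(17/18) = 1.905; 2·P(t34 > 1.905) = 6.53%.

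**Step 3: where the 1-df excess comes from.**

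| | 20 per arm | 18 per arm |
|---|---|---|
| Sandwich SE as a fraction of the unbiased SE | 0.975 | 0.972 |
| Sandwich SE with t reference | 5.6% | 5.6% |
| Unbiased SE with normal reference | 5.7% | 5.8% |
| Both (default GEE) | 6.4% | 6.5% |

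The two sources contribute about equally.

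**Step 4: closed form, 2 df.** By the same argument the Wald statistic is Hotelling's T² × n/(n − 1). It is compared with 5.991, the 95% point of chi-square on 2 df. T² converts to F on (2, 2n − 3) df by F = T² × (2n − 3)/(2(2n − 2)), and P(F > f) = (1 + 2f/(2n − 3))^(−(2n − 3)/2).
- n = 20: T² limit 5.991 × 19/20 = 5.692; f = 5.692 × 37/76 = 2.771; level (1 + 2 × 2.771/37)^(−18.5) = 7.6%.
- n = 18: T² limit 5.991 × 17/18 = 5.658; f = 5.658 × 33/68 = 2.746; level (1 + 2 × 2.746/33)^(−16.5) = 7.9%.

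**Step 5: simulation.** 20,000 null trials per setting, with independence or true working correlation. The Monte Carlo standard error is about √(0.064 × 0.936/20,000) = 0.17 points. N is the total number of subjects and k the number of interaction df.

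| Test | Week linear (1 df) | Week categorical (2 df) |
|---|---|---|
| Uncorrected sandwich, z/chi-square, 20 per arm | 6.2–6.7% | 7.1–7.7% |
| Uncorrected sandwich, z/chi-square, 18 per arm | 6.3–6.8% | 7.7–7.8% |
| Uncorrected sandwich, F(k, N − 2), both sizes | 5.4–5.9% | 5.9–6.3% |
| Mancl-DeRouen, z/chi-square, both sizes | 4.9–5.4% | 5.6–6.0% |
| Mancl-DeRouen, F(k, N − 2), both sizes | 4.2–4.7% | 4.4–4.8% |

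**Step 6: sensitivity.** Lognormal data lower the default test to 5.5–5.8% (1 df) and about 6.4% (2 df). Mancl-DeRouen with F is then conservative, at about 3.5–3.7%. Model-based standard errors gave 4.5–5.3% in the settings tried. A smaller check with a standard GEE routine (1,500 trials, exchangeable correlation, 0% or 10% missing) gave 5.4–6.8%, with Monte Carlo error of about 0.6 points.

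**The case against.** The strongest objection is that the plan is silent rather than wrong. A reader might infer that Section 9.6 commits to standard errors that are too small. It does not: it names no covariance estimator or reference distribution, and GEE appears only as an example. Model-based errors, or a corrected covariance with an F reference, would also fit the text and run at about 4–5%. This stands, and it is why the point is conditional. It does not remove the point, because the empirical sandwich is the usual way to run the named method, and model-based errors are reliable only if the working correlation is right, which the plan does not specify.

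Other stronger readings also fail:
- **That the small standard errors alone give 6–8%.** They do not. At 20 per arm they give 5.6% for 1 df, and correcting only the covariance leaves the 2-df test at 5.6–6.0%.
- **That GEE is the only method for these outcomes.** ANCOVA or Wilcoxon is named for the changes to weeks 12 and 24, so the week-12 comparison does not depend on GEE.
- **That FEV1 is worse affected because spirometry is limited to Version 2.0 enrollees.** FEV1 is exploratory (Sections 1.4.9 and 9.2.3), the GEE sentence speaks of secondary outcomes, and no document gives the number enrolled under Version 2.0.
- **That the planned confidence intervals are too narrow.** The 95% intervals in Sections 9.5 and 9.6 are per-arm summaries of change. A default GEE interval, if reported, would be about 6% too narrow at 20 per arm for 1 df (0.975 × 1.960/2.024 = 0.944).

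It is also fair to say that an excess of one to three points on nominal, unadjusted secondary tests in a pilot is small.

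**Conclusion.** The point holds in conditional form. If GEE is run with the uncorrected sandwich and a Wald z or chi-square test at 18–20 per arm, the interaction test runs at about 6–7% (linear week) or 7–8% (categorical week) against a stated 5%. The upper end needs the 2-df test, and the plan does not say how week is coded. The figures rest on normal data and a two-sided test. The correlation matters little: with complete data the closed forms do not contain it, and the simulations over 0.5–0.8 agree with them. Skewed data reduce the excess to between half a point and about one and a half points. The primary ANCOVA and the ANCOVA or Wilcoxon comparisons are untouched. Low priority, but worth correcting because the named method in its usual form misses the stated error rate and the remedy is simple.

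**What to change.** Add a sentence to Section 9.6: GEE analyses of continuous outcomes will use a bias-corrected sandwich covariance (for example Mancl-DeRouen or Kauermann-Carroll) together with a t or F reference distribution. Both parts are needed. State the working correlation and whether week is linear or categorical in the same place.

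A mixed model for repeated measures with Kenward-Roger degrees of freedom is an acceptable alternative; Section 9.6 already plans a mixed model for the crossover data. Neither that model nor Kauermann-Carroll was simulated here; the corrected levels above are for Mancl-DeRouen.

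The cost is a software option and slightly wider intervals. Mancl-DeRouen with F is a little conservative (4.2–4.8% for normal data, about 3.5–3.7% for lognormal data), so a suitable transformation of skewed markers, which Section 9.5 already foresees for the primary outcomes, would also help here.

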6.0 CLINICAL AND LABORATORY EVALUATIONS

6.1 Schedule of Events (SOE)

| Evaluation | Screening | Pre-Entry ¹ | Entry | Week | | | | | | | | Premature Treatment and/or Study Discontinuation | | |
|--|-----------|------------------------|-------|------|---|---|----|----|----|----|----|--|----|----------------|
| | | | | 2 | 4 | 8 | 12 | 14 | 16 | 20 | 24 | | 28 | |
| Documentation of HIV-1 infection | X | | | | | | | | | | | | | |
| Medical History/Medication History | X | | | | | | | | | | | | | |
| Complete Physical Exam | X | | | | | | | | | | | | | |
| Targeted Physical Exam | | X | X | | X | X | X | | X | X | X | X | | X |
| Clinical Assessments | | | X | | X | X | X | | X | X | X | X | | X |
| Concomitant Medications | | X | X | | X | X | X | | X | X | X | X | | X |
| Hematology | X | | X | | | | X | | | | X | | | X |
| Liver Function Tests/Blood Chemistries | X | | X | | X | | X | | X | | X | | | X |
| Fasting Lipid Panel | | | X | | | | X | | | | X | | | X |
| Plasma HIV-1-1 RNA | X | | X | | | | X | | | | X | | | X |
| CD4+/CD8+ | X | | X | | | | X | | | | X | | | X |
| Pregnancy Test | X | | X | | X | X | X | | X | X | X | X | | X |
| Prothrombin time/INR/PTT ² | | X | | | | | | | | | | | | |
| Hepatitis B and C | X | | | | | | | | | | | | | |
| Stored Plasma for Immunology/Virology ⁵ | | X | X | | X | | X | | X | | X | X | | X |
| Stored PBMC for Immunology/Virology ⁵ | | X | X | | X | | X | | X | | X | X | | X |
| Urine adenosine level (stored) ⁵ | | | X | | X | | X | | X | | X | | | X |
| Serum for Dipyridamole concentration (stored) | | | | | X | X | X | | X | X | X | | | X |
| Brachial Artery FMD | | | X | | X | | X | | | | X | | | X ³ |
| Rectal swabs for GC/CT NAAT ² | X | | X | | | | X | | | | X | X | | |
| HSV Serology ² | | | X | | | | | | | | | | | |
| Flexible sigmoidoscopy (rectal biopsy) ^{2, 5} | | | X | | | | X | | | | X | X | | |
| Adherence self-report | | | | | X | | X | | X | | X | | | |

| Evaluation | Screening | Pre-Entry ¹ | Entry | Week | | | | | | | | Premature Treatment and/or Study Discontinuation | |
|--|-----------|------------------------|-------|------|---|---|----|----|----|----|----|--|----|
| | | | | 2 | 4 | 8 | 12 | 14 | 16 | 20 | 24 | | 28 |
| Medication Adherence Assessment ⁴ | | | X | | X | | X | | X | | X | | |
| Telephone assessment of tolerability/adherence | | | | X | | | | X | | | | | |
| Pre- and post-bronchodilator spirometry ⁶ | | | X | | X | | X | | | | X | | |

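### As worded, the longitudinal model for secondary outcomes in 9.6 makes no use of the randomised baseline, so its week-12 contrast is less precise than a baseline-adjusted one, and 9.6 does not say which analysis gives the week-12 estimate

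*Combined protocol and SAP*

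**What the plan says.** Section 9.6 first gives secondary and exploratory endpoints a simple between-arm comparison: "As in the primary analysis, between-arm comparisons will be made using either an ANCOVA model or the Wilcoxon rank sum test". It then adds: "For secondary outcomes with more frequent measurements (i.e. baseline, 4, 12 week), longitudinal models such as Generalized Estimating Equations (GEE) will be used". The stated purpose is to compare the arms' trajectories over time. The terms follow: "Included in the model will be predictor variables for week, treatment group, and their interaction". Section 9.6 names no baseline covariate, no CD4 term and no constraint that the arms share a baseline mean. It does not say whether week is a category or a straight line, which working correlation is used, or whether this model replaces the ANCOVA or is run beside it.

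The primary ANCOVA in 9.5 does adjust. It "compares the outcomes at 12 weeks between arms (placebo/DP) after adjusting for baseline activation (or plasma level) and CD4 cell count". Section 9.4 counts on that adjustment for power: "it's likely that there will be sufficient power to detect even smaller effects than what is expected".

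The Schedule of Events (6.1) has "Stored Plasma for Immunology/Virology", stored PBMC and brachial FMD at entry, week 4 and week 12. These are the sources of most of the marker and FMD secondary endpoints in 9.2.2.

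**The concern.** Randomisation makes the two arms' expected baseline values equal. A model that gives each arm a free baseline mean ignores this and estimates the baseline difference from the data. The noise in that estimate passes into the week-12 contrast. ANCOVA avoids this, and so does a longitudinal model with a common baseline mean.

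With 18 to 20 subjects per arm and each secondary test at a nominal 5%, precision is scarce. Section 9.4 expects adjustment to help, yet the longitudinal model leaves it out. A second problem follows: an endpoint with a week-4 value could carry one week-12 estimate from the ANCOVA and a different one from the GEE, with no rule for choosing between them.

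**Working it through.** **1. The plan's own figure.** Inputs from 9.4 and 9.5: 20 or 18 per arm, two-sided 5%, 80% power. A two-sample t-test (noncentral t) gives power 0.7999 for a standardised difference of 0.909 with 20 per arm, and 0.7998 for 0.961 with 18 per arm. Multiplying by the stated SD of 0.54 gives 0.909 × 0.54 = 0.491 and 0.961 × 0.54 = 0.519, which match the stated 0.49 and 0.52 (× 10⁶ pg/mL). The figures reproduce, with no covariate adjustment in them.

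**2. What the 9.6 model estimates.** Three visits by two arms make six means. Categorical week, arm and their interaction use six parameters, so the mean model is saturated. With complete data the week-12 interaction is therefore

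(mean at week 12 − mean at baseline) in the DP arm, minus the same in the placebo arm.

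In GEE fits with an exchangeable working correlation to simulated trials (20 per arm, 300 runs at each rho), the two agreed to within 3 × 10⁻¹⁶ every time.

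**3. Variances.** Let σ be the SD at each visit and n the number per arm.

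- Difference in change: 2(1 − rho) σ² × 2/n
- Baseline-adjusted (ANCOVA): (1 − rho²) σ² × 2/n
- Ratio: 2(1 − rho) / [(1 − rho)(1 + rho)] = 2/(1 + rho)

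Example at rho = 0.5: 2 × 0.5 = 1.00 against 1 − 0.25 = 0.75, a ratio of 1.33.

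**4. Power with 18 per arm.** The documents give no rho, so a range is assumed. For each rho the effect is set where ANCOVA (33 degrees of freedom) has 80% power. The difference in change (34 degrees of freedom) is then evaluated at that effect. The last two columns are detectable differences at 80% power, in units of σ.

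| rho (assumed) | Variance ratio | Power, difference in change | Detectable, change | Detectable, ANCOVA |
|---|---|---|---|---|
| 0.3 | 1.54 | 62% | 1.137 | 0.918 |
| 0.5 | 1.33 | 68% | 0.961 | 0.833 |
| 0.7 | 1.18 | 73% | 0.745 | 0.687 |
| 0.8 | 1.11 | 76% | 0.608 | 0.577 |
| 0.9 | 1.05 | 78% | 0.430 | 0.419 |

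Below rho = 0.5, 2(1 − rho) exceeds 1, so the difference in change is noisier than comparing week-12 values with no use of baseline at all.

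**5. Does the remedy recover the precision?** Simulated variances of the week-12 contrast (20 per arm, σ = 1):

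| rho | As written | ANCOVA | Common baseline mean |
|---|---|---|---|
| 0.5 | 0.096 | 0.077 | 0.076 |
| 0.7 | 0.056 | 0.048 | 0.047 |
| 0.9 | 0.0194 | 0.0189 | 0.0188 |

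The common-baseline model matches ANCOVA. These fits used an exchangeable working correlation. Under working independence the common-baseline contrast would reduce to the raw week-12 difference, with variance σ² × 2/n = 0.100, and the gain would be lost.

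**The case against.** The strongest reply is that the adjusted week-12 comparison is already planned. The sentence before the GEE sentence gives these endpoints an ANCOVA or Wilcoxon test in the manner of the primary analysis, and the longitudinal model is described as a comparison of trajectories, for which a week-by-arm interaction is a standard and valid tool. This largely stands. A reader might infer that secondary endpoints in general lose power; the documents do not support that, because 9.6 never says that the GEE replaces the ANCOVA. What remains is that 9.6 does not say the opposite either, and leaves open which week-12 estimate counts.

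It is also fair that GEE is offered as an example, that the list of terms is not said to be exhaustive, and that baseline as an outcome row is inferred from the listed visits and the absence of a baseline covariate. It is the natural reading, but not an explicit statement.

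The size can be overstated. At the plan's own 0.961 SD with 18 per arm, the difference in change and ANCOVA have power 66% and 84% at rho 0.3, 80% and 90% at 0.5, 95% and 98% at 0.7, and over 99% for both at 0.8. The loss is material at low to moderate correlation and small at high correlation.

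A reader might also infer a larger loss from entering week as a straight line: 51%, 56% and 62% power at rho 0.3, 0.5 and 0.7. That needs a coding that 9.6 does not state and an effect already complete by week 4. If the effect grew linearly, the same model would have 63%, 70% and 75%, slightly better than categorical week.

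Finally, spirometry also has a week-4 visit, but FEV₁ is exploratory in 9.2.3, while the GEE sentence refers to secondary outcomes. Stored week-4 samples show that the assays are possible, not that each will be run.

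**Conclusion.** The point holds in a limited form. On its natural reading, the 9.6 longitudinal model gives an unadjusted difference in change at week 12, exactly so with categorical week and complete data. Relative to a baseline-adjusted analysis the variance is 1.54 to 1.05 times as large for rho from 0.3 to 0.9, and power is 62% to 78% where ANCOVA has 80% with 18 per arm. The range of rho is an assumption, and the variance formulas take equal SDs at baseline and week 12.

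A reader might take this as biased secondary results or as a flaw in the main analysis. Neither follows. The arms are randomised, so the contrast remains valid, and the ANCOVA for sCD14, sCD163 and IL-6 and its sample size are unaffected. If the GEE supplies the week-12 test, power is lost; if it is supplementary, the defect is two differing week-12 estimates with no stated precedence. Either way, 9.6 needs a short clarification that also gains precision from data already collected.

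**What to change.** In the longitudinal model of 9.6:

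- Treat week as a category.
- Either keep baseline as an outcome and constrain the arms to one common baseline mean, or make weeks 4 and 12 the outcomes with the baseline value, by week, as a covariate.
- Include CD4 count, as in 9.5.
- State the working correlation. For the common-baseline version it must not be independence.
- Say which analysis gives the week-12 between-arm estimate for each secondary endpoint, and label the other as supportive.

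The cost is a few sentences and no new data. Section 9.7 says that the immune activation measurements are run in batch after follow-up ends, so the wording can be settled before those results exist. There is a small downside: a few extra model terms with about 36 to 40 subjects. The covariate version also drops anyone without a baseline value, while the common-baseline version keeps every subject with any data.
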